Study Visits #2-#13 -- Group Prenatal Yoga Classes and Home Activities: Participants will engage in 12 weeks of weekly community-based group prenatal yoga classes (75 minutes each) and self-directed daily home practice. The 75-minute gentle prenatal yoga group class will be taught by experienced yoga teachers familiar with teaching yoga-na~~ve~~ and pregnant individuals; only study participants will take part in these classes. All prenatal yoga teachers will use a manual during the study with options of sequences of gentle yoga movements, breathing practices, and relaxation practices appropriate for pregnancy (excerpt of manual provided). Participants and study staff will follow the guidelines for prenatal exercise of ACOG which advises the cessation of activity if a participant experiences vaginal bleeding, dizziness, increased shortness of breath, chest pain, headache, muscle weakness, calf pain or swelling, preterm labor/delivery (regular, frequent, painful contractions), decreased fetal movement, or fluid leaking from the vagina (see Human Subjects), assessed at the beginning of each class and in the weekly phone calls, without the participant first consulting with their healthcare provider.¹⁵³ If a participant is advised by their healthcare provider to minimize physical activity but is still allowed to do yoga, the yoga instructors will advise the participant how to safely modify their practice in class.

Home activity: participants will be encouraged to apply SM skills to engage in home-based PA. A handbook of yoga poses practiced during the intervention group sessions and suggestions for other PA (e.g. walking, stair climbing, dancing, among others) will be provided for participants~~to~~ use. Participants will keep a home log of their symptoms and their participation in home PA, which serves as a tool for self-monitoring of symptoms and documenting use of SM skills.^{108,114} (the home log is available in the Study Instruments document) Participants who are comfortable with computers will be able to complete the home logs through RedCap; those who are not will receive pen/paper logs to take home with them which will be collected weekly by RAs.

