Weekly contact by study staff (phone or email per participants' choice): Study staff will maintain regular contacts in the mode of participants' choice during the 12 weeks of the intervention. This is intended to help with retention as well as monitoring for adverse events. Study staff will collect data about minutes of physical activity during these weekly phone contacts. No survey or other data will be collected during this contacts, unless a participant verbalizes a physical or psychological adverse event.

Study Visit #7 (Intervention Week 6): Participants will be asked to complete questionnaires at the midpoint of the 12-week intervention at home electronically (if they have computer access at home) or in paper/pencil form (for those without sufficient comfort levels or access to a computer~~to~~RA will pick them up at participants~~to~~ next class).

Study Visit #14-- Last visit during pregnancy: Participants will complete another set of questionnaires electronically or in paper/pencil format. A blood sample will also be collected (8 ml blood by venipuncture in 2 EDTA [purple top] tubes).

Study Visit #15-- Postpartum Visit/Interview Session: Each participant will meet with study staff (RA, PD, and/or PI) to complete the questionnaires and participate in a semi-structured interview. Specific questions for this semi-structured interview are found in the Study Interview Guides/Scripts document. This interview will be audiotaped (and later transcribed).

Note: if a participant chooses to withdraw from the study, they will be given the opportunity to give their reasonings for withdrawal in the form of a short interview with research staff.

**** For Addendum Feb 2018: "Long-Term Follow-Up" study visit:** participants who "opted-in" to being contacted for future study will be contacted via email and/or phone about answering survey questions. Participants will give consent via REDCap (or in rare instances, may choose paper & pencil, which will be completed in-person with the research nurse) and will answer survey questions, using the same measures that have been used at previous study visits.

STUDY MEASURES

** SEE TABLE 1. STUDY MEASURES BY TIMEPOINTS

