above. Findings from this specific aim will provide important preliminary data for future explorations of epigenetic factors involved in treatment response.³⁹

RETENTION AND ADVERSE EVENT MONITORING:

Participants will be contacted weekly by the PD or RA (in the format preferred by participant: phone, text, email) to enhance retention, monitor for any adverse events, and schedule study visits. No data will be collected during these contacts. Participants will be asked if they have any physical or psychological concerns that have arisen and action will be taken if necessary. See protocol for adverse event monitoring in uploaded documents.

5. Upload any supporting tables or documents (e.g. protocol documents, figures/tables, data collection forms, study communications/reminders):

ID: MS8_HM20006941

View: SF - Study Activities

Study Activities

1. * Select which study type best describes the majority of the study. Your response will help determine which IRB panel should review this:

- Bio-Medical
-
- Qualitative - Social/Behavioral/Education (SBE)
-
- Quantitative - SBE
-
- Mixed Method - SBE
-
- Mixed Method - Biomedical
-

2. * This study will involve (check all that apply):

- procedures such as surveys, interviews, field studies, focus groups, educational tests, deception, psycho-physiological testing, any other similar data collection
-
- secondary data analysis: procedures such as analysis of information collected for non-research purposes (includes both retrospective and prospectively collected information), or analysis of data previously collected for a prior research study
- drugs, devices, experimental interventions, biohazards, radiation, other medical or surgical procedures
-

ID: MS8_HM20006941

View: SF - Bio-Med Project Details

Bio-Med Project Details

1. * Select all details that apply:

- Drugs, Biologics, Supplements, and/or Other Compounds
-
- Placebo
-
- Washout Period
-

Device Evaluation

Bio-Hazards, Other Toxins, Recombinant DNA/Gene Transfer

Radiation Exposure and/or Scans involving radiation (PET, MRA)

Stem Cells

Expanded Access - Treatment Use of an Investigational Product

Other Medical or Surgical Procedures

Protected Health Information (PHI)

ID: MS8_HM20006941

View: SF - Social/Behavioral Project Details

Social/Behavioral Project Details

1. * Select all that apply to this study:

Analysis of Information Originally Collected for Non-Research Purposes

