To minimize risk of physical harm, all study staff and prenatal yoga teachers will be trained about the American College of Obstetricians and Gynecologists guidelines for exercise in pregnancy. Participants will be advised to stop practicing the yoga-based physical activity if they experience: vaginal bleeding, dizziness, increased shortness of breath, chest pain, new acute headache, muscle weakness, calf pain or swelling, uterine contractions, decreased fetal movement, or fluid leaking from the vagina.¹² Our obstetrician collaborator ([name]) will be on call to counsel participants about appropriate treatment options should they experience physical distress.

4. * Describe how the risk is the least possible for achieving the objectives of the research [45 CFR 46.204(c)]:

We believe that most serious risks (e.g., loss of confidentiality, risk of physical harm) to participants are very unlikely. While some risks may be more likely to occur (e.g., minor, transient psychological distress), these risks are much less serious. Therefore, the potential benefits of the proposed study outweigh the potential risks of this study for the individual participants. The potential risks are counterbalanced by the knowledge that they are contributing to the body of knowledge regarding self-management of depression during pregnancy. Participants may choose to withdraw at any point from the study.

This study will provide information about the feasibility, acceptability, and preliminary effects of a biobehavioral self-management approach for perinatal depressive symptoms. This line of research will contribute to the body of knowledge about adjunctive therapies for depressive symptoms in pregnancy, a serious problem which contributes to poor maternal-child outcomes. Ultimately, this will contribute to the development and implementation of theoretically driven depression prevention/ resiliency building interventions and measurement of appropriate biobehavioral outcomes to determine the effectiveness of interventions.

5. Describe how consent will be obtained from the pregnant woman if the research may:

_directly benefit the pregnant woman or the pregnant woman and the fetus, or
_offer no benefit for the woman nor the fetus (when risk to the fetus is not greater than minimal) and the purpose of the research is the development of important biomedical knowledge that cannot be obtained by any other means [45 CFR 46.204(d)]:

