1.3.5. Risk of participant burden: Participants will have the burden of travel for study visits. It is acknowledged that there is a long list of items that make up the prenatal and postpartum questionnaires, but, to decrease patient burden, instruments have been chosen that are short and easily self-administered. The specimen collection is estimated to take approximately 5 minutes during the collection visits.

1.3.6. Risk of physical harm: There is a small risk of physical injury associated with physical activity, even gentle forms such as prenatal yoga. However, the gentle prenatal yoga group classes will be taught by experienced yoga teachers familiar with teaching yoga-naive and pregnant individuals. The classes are designed for people of any fitness level and experience with yoga is not needed. Preliminary studies suggest that gentle yoga-based physical activity, when taught by a prenatally-certified instructor, is safe during pregnancy, even in high-risk populations.^{5,10,11}

2. * Describe how the risks / harms will be minimized:

2. Adequacy of Protection against Risks

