All study team members will be poised to establish community referrals as needed (e.g. Henrico County Community Services Board: [contact]; Chesterfield County Community Services Board: [contact]; Richmond Behavioral Health Authority: [contact]; local emergency departments).

Protections against risk associated with specimen collection: The risks associated with drawing blood will be minimized by having staff with training in phlebotomy to perform the blood draw.

Protections against risk associated with participant burden: To decrease participant burden, instruments have been chosen that are short and easily self-administered. The blood specimen collection is estimated to take approximately 5 minutes during the appropriate study visits and will be conducted by well-trained personnel.

Protections against risk of physical harm: To minimize risk of physical injury, the prenatal yoga class teachers are certified

to teach yoga modified for pregnancy. Participants will be advised to not participate in yoga if they experience: vaginal bleeding, dizziness, increased shortness of breath, chest pain, new acute headache, muscle weakness, calf pain or swelling, preterm labor/delivery (regular, frequent, painful contractions), decreased fetal movement, or fluid leaking from the vagina, without first consulting with their healthcare provider (per guidelines from the American College of Obstetricians and Gynecologists about when not to exercise in pregnancy).¹² These symptoms are not considered adverse events attributable to yoga but would preclude a participant for engaging in yoga. Our obstetrician collaborator ([name]) will be on call to counsel participants about appropriate treatment options should they experience physical distress.

- 3. If the disclosure of any of the information obtained during the study would place the individual at risk for harm (legal, reputation, emotional etc.) and the information will be recorded so that the individual could be identified, explain the protections that will be put in place to decrease the risk of disclosure:**
- 4. * The Code of Virginia requires that most medical personnel and all employees of institutions of higher education report suspected child/elder abuse or neglect. Is it likely investigators could discover information that would require mandatory reporting by the investigators or staff:**

Yes
 No

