- 8. * Describe criteria for withdrawing an individual participant from the study; such as safety or toxicity concerns, emotional distress, inability to comply with the protocol, etc.:**

We do not anticipate withdrawing a participant from the study, unless she (a) is no longer pregnant due to spontaneous or therapeutic abortion prior to the end of the 12 week intervention period, or (b) she is unable to comply with the protocol and attend a majority of the study sessions, or (c) participant reports any of the following and are advised to cease gentle yoga-based physical activities by their healthcare provider: new vaginal bleeding, new dizziness, new/increased shortness of breath, chest pain, new acute headache, new calf pain/swelling, preterm labor/ delivery (regular, frequent, painful contractions), decreased fetal movement, new fluid leaking from the vagina.

- 9. * Summarize any pre-specified criteria for stopping or changing the study protocol due to safety concerns:**
Participants will be asked to stop engaging in the prenatal yoga classes if they experience any of the symptoms identified by ACOG as reasons to cease physical activity (list in item #8 above). See DSMP.

- 10. Where appropriate, discuss provisions for ensuring necessary medical, professional, or psychological intervention in the event of adverse events to the subjects:**
see data safety monitoring plan

11. * Describe any potential for direct benefits to participants in this study:

We cannot guarantee any direct benefits to participants in the study. The research may yield new knowledge about biobehavioral self-management approaches as adjunctive therapies for perinatal depressive symptoms.

12. * Describe the scientific benefit or importance of the knowledge to be gained:

This study will provide information about the feasibility, acceptability, and preliminary effects of a biobehavioral self-management approach for perinatal depressive symptoms. This line of research will contribute to the body of knowledge about adjunctive therapies for depressive symptoms in pregnancy, a serious problem which contributes to poor maternal-child outcomes. Ultimately, this will contribute to the development and implementation of theoretically driven depression prevention/ resiliency building interventions and measurement of appropriate biobehavioral outcomes to determine the effectiveness of interventions.

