13. If applicable, describe alternatives (research or non-research) that are available to potential participants if they choose not to participate in this study:

14. * Indicate if this study will have a Data Safety Monitoring Board (DSMB) or a Data Safety Monitoring Plan (DSMP): [Required for all greater than minimal risk studies]

DSMB

DSMP

No DSMB/DSMP [Note: This response is not applicable for greater than minimal risk studies]

ID: MS8_HM20006941

[View: SF - DSMP Details](#)

DSMP Details

1. * Describe your Data Safety Monitoring Plan for monitoring the data collected to ensure the safety of participants:
please see DSMP document attached

ID: MS8_HM20006941

[View: SF - Consent Qualifiers](#)

Consent Qualifiers

1. * Are you submitting your study as exempt and therefore no consent is required:

Yes
 No

ID: MS8_HM20006941

[View: SF - Consent Groups](#)

Consent Groups

1. * List all consent groups:

Group	Types	Waivers	Roles	Roles - Other	Consent	Coercion	Decision	Re-Consent
View Waiver to view	None of the Above (select)	Waiver of Some or All	Research Nurse		Waiver of consent to be	If a woman is interested in	The potential	

Group	Types	Waivers	Roles	Roles - Other	Consent	Coercion	Decision	Re- Consent

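### To the extent it governs, one sentence rules out in advance classing ten listed symptoms as yoga-related, even when they start during or soon after a session

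*Combined protocol and SAP*

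**What the plan says.** The paragraph on physical harm (Risks, Discomforts, Potential Harms and Benefits, item 2, section 2.2) lists ten symptoms, citing obstetric guidance on exercise in pregnancy. A woman who has one is advised not to do yoga until she has spoken to her provider. The paragraph then says: "These symptoms are not considered adverse events attributable to yoga but would preclude a participant for engaging in yoga". It gives no exception for time of onset, severity or individual causality.

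Other places bear on this:

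- Research Description, item 4, Study Visits #2-#13, gives the same ten symptoms as reasons to cease activity and has them "assessed at the beginning of each class and in the weekly phone calls".
- Pregnant Women or Fetuses, item 3: "Participants will be advised to stop practicing the yoga-based physical activity if they experience: vaginal bleeding, dizziness, increased shortness of breath", with the list continuing to ten items.
- Risks, item 8, makes such symptoms grounds for withdrawal when the provider advises stopping. That list opens: "new vaginal bleeding, new dizziness, new/increased shortness of breath, chest pain, new acute headache, new calf pain/swelling". Item 9 points to it for stopping classes.
- Risks 1.3.6 accepts a physical risk: "There is a small risk of physical injury associated with physical activity, even gentle forms such as prenatal yoga".
- Weekly contact by study staff: "No survey or other data will be collected during this contacts, unless a participant verbalizes a physical or psychological adverse event". The Retention and Adverse Event Monitoring paragraph gives adverse-event monitoring as one purpose of the weekly contacts, yet says without exception that no data are collected at them.
- Adverse-event handling is sent elsewhere: "See protocol for adverse event monitoring in uploaded documents" in that same paragraph, and "please see DSMP document attached" under DSMP Details. Neither text was available for this review.

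**The concern.** Whether an event is related to an intervention is normally judged from the case: when it began, what the woman was doing, and what else explains it. Here the answer is fixed beforehand for a whole class of symptoms. Three of them (preterm labor, decreased fetal movement, leaking fluid) bear directly on the protocol's expectation, under Pregnant Women or Fetuses, that the intervention carries no risk to the fetus. Others (muscle weakness, dizziness, calf pain) could be signs of exertion or strain. That is a clinical inference and is not stated in the protocol.

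The study has one group and no concurrent control, and it is meant to inform later studies. If the sentence sets the classification, a report of no yoga-related events of these types would read as reassurance when it could not have come out otherwise.

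**Working it through.** The plan gives no figure on this point. The check sets the four symptom lists side by side and asks what follows.

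| Place | Symptoms | Use | Timing implied |
|---|---|---|---|
| Section 2.2 | 10 | No yoga before consulting provider; not attributable to yoga | None stated |
| Study Visits #2-#13 | Same 10 | Cease activity; checked at class and weekly | During the 12 weeks |
| Pregnant Women or Fetuses, item 3 | 10, with contractions in place of preterm labor | Stop practising | During practice |
| Risks, item 8(c) | 9, all on the section 2.2 list | Withdrawal on provider advice | After entry |

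**Counts.** In item 8(c), six symptoms carry the word new (bleeding, dizziness, breathlessness, headache, calf pain or swelling, leaking fluid) and three do not (chest pain, preterm labor, decreased fetal movement): 6 + 3 = 9. Muscle weakness is the one section 2.2 item that is absent: 9 + 1 = 10.

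**Does the sentence reach symptoms that begin during the programme?** It sets no time limit. A rule to stop practising applies to someone who is already practising, and a withdrawal rule for new symptoms applies to someone already enrolled. The protocol therefore expects such onset, and nothing in the available text takes it out of the sentence's scope.

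**What follows.**

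- *If section 2.2 governs:* the number of listed symptoms classed as yoga-related is 0, whatever the true number. Since 9 of the 9 symptom grounds for withdrawal are on the list, no withdrawal on those grounds could be labelled related.
- *If the DSMP or adverse-event protocol governs and requires case-by-case review:* classification is unaffected. What remains is a sentence in the application that contradicts it.

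**Illustration only.** The documents give no event rates. Let p be the true rate of yoga-related listed symptoms per woman and s the share recognised on review, with women independent. The chance that at least one of 41 women is classed as related is 1 − (1 − p × s)^41.

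| Assumed p | s = 0.5 | s = 1 |
|---|---|---|
| 2% | 33.8% | 56.3% |
| 5% | 64.6% | 87.8% |
| 10% | 87.8% | 98.7% |

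Under section 2.2, s = 0 and the chance is 0%, which only restates the premise. Both p and s are assumed, and the formula leaves out unrelated symptoms wrongly judged related. The table shows how the rule works; it does not estimate what this study would lose.

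**The case against.** The strongest reply is that section 2.2 answers an ethics-form question about minimising risk and is not where relatedness rules would be expected. The Documents page lists a DSMP and a Protocol for Adverse Event Monitoring, both approved, and either may already require individual attribution. This stands: the practical effect cannot be established from the available text.

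Second, the sentence can be read narrowly, as separating contraindications to exercise from injuries caused by it. The check at the start of each class fits that reading. But the sentence does not say so, and the stop-practising and withdrawal rules use nearly the same list for symptoms that arise later. The narrow reading softens the point without removing it.

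Third, the tension with Risks 1.3.6 is modest. That section concerns physical injury, and section 2.2 does not put injury beyond attribution. The overlap rests on the clinical inference noted above.

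Fourth, case-by-case review has its own error. Without a concurrent control, some ordinary pregnancy symptoms will be judged related. This stands and shapes the fix.

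A reader might go further and infer that these symptoms go unrecorded, or that women are less protected. The documents do not support that. Symptoms are checked at each class, the weekly contacts exist partly to monitor adverse events, yoga stops when symptoms occur, an obstetrician is on call, and the DSMB has access to de-identified data. Nor is feasibility or acceptability compromised, since no Aim 1 measure depends on attribution.

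**Conclusion.** The point holds as a low-severity defect of wording whose consequence is conditional. That the sentence is unqualified, covers ten symptoms, and sits beside rules expecting their onset during the programme is certain from the text. That it would decide any classification is an assumption that only the DSMP and the adverse-event protocol can settle. If it does, a related-event count of zero for these types carries no information, while overall counts by timing would still be informative. If it does not, the effect on classification is nil and only the contradiction needs removing. The assumed-rate probabilities carry no weight in this conclusion.

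**What to change.** - In section 2.2, delete the attribution clause and keep the statement that the symptoms preclude yoga. Leave the stopping and withdrawal rules as they are.
- State that relatedness of any listed symptom with onset after the first session is judged case by case under the DSMP, using onset relative to the last class or home session. The on-call obstetrician collaborator is preferable to the PI alone, who would otherwise be judging the PI's own intervention.
- Make counts available to the DSMB both overall and as judged related, and report them together, since the judged-related count may include unrelated pregnancy symptoms.
- Give the Retention and Adverse Event Monitoring paragraph the adverse-event exception already in the Weekly contact paragraph, so that onset can be recorded at those contacts.

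**Cost.** One clause is deleted, one exception is added, and each event needs an onset time and a judgment, using existing contacts and staff. Workload depends on rates not given. If 10%, 50% or 90% of 41 women reported a listed symptom, 41 × 0.10 = 4.1, 41 × 0.50 = 20.5 or 41 × 0.90 = 36.9 women would need at least one judgment. The safety summary may look less favourable. If the DSMP already requires individual attribution, only the wording of section 2.2 and the Retention paragraph needs to change.
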